All Veterans enrolled in the study will be beginning a course of either Prolonged Exposure (PE) or Cognitive Processing Therapy (CPT), which will be delivered as usual by PTSD clinical staff. As the BFI is an adjunctive intervention, Veterans' trauma-focused treatment is considered separate from the present study. The Veterans will be seen by regular clinical staff and no artificial limits will be imposed upon their treatment, although treatment engagement will be tracked (see Assessment section, below). Veterans and their family members will be recruited for the present study at the beginning of a course of treatment at the clinic. Phase I will be an open pilot trial of 4 dyads. All family members in Phase I will receive the BFI, which will be delivered as 2 weekly 50-minute sessions of the BFI, consistent with the application with the BFI in previous work (Thompson-Hollands et al., 2015). Phase II will include 20 dyads (N=40) using identical recruitment, inclusion/exclusion criteria, and assessment structure; however, in this second phase family members will be randomly assigned to receive or not receive the BFI, and VABHS clinicians will deliver the BFI sessions (rather than the PI as in Phase I).

Veterans:

Inclusion criteria.

- (1) has a current diagnosis of PTSD

(2) is 18 years of age or older

(3) has an eligible family member (defined as a spouse/significant other, parent, adult child, sibling, etc., 18 years of age or older who currently has substantial daily or weekly contact with the Veteran)

(4) is beginning a course of either CPT or PE at VA Boston.

Exclusion criteria.

(1) has current diagnoses of unstable bipolar disorder, past or present psychosis, or organic mental disorder

(2) has clear and current suicidal risk (assessed via the MINI-Suicide Module (Sheehan et al., 1998), see Assessment section below)

(3) has current moderate or severe substance use disorder

(4) is currently participating in family-based therapy/couples-counseling

Family members:

Inclusion criteria.

(1) is 18 years of age or older

(2) is the family member (defined as a spouse/significant other, parent, adult child, sibling, etc.) of the Veteran

(3) currently has substantial daily or weekly contact with the Veteran

Exclusion criteria.

(1) has a current diagnosis of PTSD

(2) has current diagnoses of unstable bipolar disorder, past or present psychosis, or organic mental disorder

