(2) has clear and current suicidal risk (assessed via the MINI-Suicide Module (Sheehan et al., 1998), see Assessment section below)

(3) has current moderate or severe substance use disorder

(4) is currently participating in family-based therapy/couples-counseling

Recruitment of Veterans and family members will occur through the VABHS outpatient mental health clinics (e.g., the PTSD Clinic, the Women's Clinic, General Mental Health, Center for Returning Veterans, etc.). All interested participants will be contacted by the PI for a phone screen, where the study and its procedures will be described and a short screen for eligibility will be administered. If the initial screening requirements are met, participants will be invited to an in-person assessment. During the first appointment, the Veteran and family member will be provided with a thorough description of the project and the informed consent form will be reviewed and signed. Baseline assessment measures will then be administered (see Assessment section).

Veterans will proceed with PE or CPT as usual through the clinic, with no restrictions or limitations. Should a Veteran choose to discontinue PE or CPT, he or she will continue to be enrolled in the proposed study for follow-up assessments, as treatment drop-out is a variable of interest. All family members who are to receive the BFI (i.e., all family members in *Phase I* and half of family members in *Phase II*) will participate in the two BFI sessions, and then move into the follow-up portion of the study.

BFI: The BFI is a 2-session individual intervention delivered by a clinician to the adult family member of a Veteran with PTSD who is beginning a course of CPT or PE treatment. The BFI sessions are guided by a manual, which has previously been developed by the PI but will

be revised for the purposes of the current study as described earlier to enhance its relevance to the families of Veterans with PTSD. The BFI may be completed either in person or remotely via telephone.

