The codes that link the names of participants and their ID numbers will be kept confidential by the PI in a secured cabinet located within the PI's office (JP campus, room 13B-60) (or, during construction on the 13th floor of Building 1 in JP, in a secure basement storage area appropriate for materials containing PII). Collected data forms will be in a locked file cabinet located in the PI's office (or, during construction on the 13th floor of Building 1 in JP, in a secure basement storage area appropriate for materials containing PII). These data are accessible to the PI and personnel working on the project. Data will be entered electronically by trained staff, and data entry discrepancies will be corrected by the data entry supervisor based on source documents. The quality of the data will be monitored quarterly. Data will be securely transmitted using VA approved methods.

Audio recordings will be captured using Philips recorders with FIPS 140-2 validated encryption. Recordings may be obtained while study staff are teleworking; in these cases the recorders will be stored in the home in a locked cabinet/drawer that is only accessible to the study staff member. Recorders will be hand-carried to the VA as soon as it is feasible and safe to do so, at which point the recordings will be uploaded to the PI's personal research drive behind the VA firewall and deleted from the recording device.

The primary outcomes measures will be CAPS-5 total scores and ratings of homework completion (from the Homework Completion Scale), and number of sessions attended/dropout. Data quality will be monitored by inspection of the completed forms by the research assistant and any problems detected will be discussed with the PI. All assessors will be fully trained on the assessment measures, per the usual training procedures within BSD. Adherence to the intervention will be monitored using recordings of sessions and weekly supervision, as described previously. If diagnostic and/or intervention drift is observed, staff will be retrained until acceptable reliability is reached.

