Overview of data analysis: Quantitative data analysis will be performed using MPlus and SPSS, and NVivo management software will be used for qualitative data. Prior to full data analysis, the balance of randomization will be checked and unbalanced factors between groups will be controlled for in subsequent analyses. Similarly, all major variables will be assessed for skewness and outliers, and in cases where parametric analytic assumptions are violated we will use transformations. Preliminary analyses will consist of descriptive statistics by assessment period. All quantitative outcomes will be tested at a two-sided $\alpha=.05$ level.

Data checking: Standard data checking procedures will include checking forms for missing data, double entry with discrepancy resolution, daily back-up copies of computer files, and examination of key variables for skewness, variability, missing data, and outliers. Data will be transformed to achieve normality if needed. If any outcome variable is too zero-inflated to allow for transformation, it will be analyzed with logistic regression or generalized estimating equation techniques (appropriate for this small pilot study).

Missing data: We will make every effort to retain participants, but as treatment engagement is a key outcome of the present study we will also carefully tabulate and report dropout rates and patterns in the present study, including exact timing of dropout. Multilevel regression models will be used to evaluate treatment outcomes; this approach is robust to missing data and is considered "state of the art" for use with unbalanced data sets due to treatment dropout (Schafer & Graham, 2002). There are also several methods for correcting biases due to missing data when using a multilevel regression approach (e.g., pattern-mixture modeling).

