Power analyses: Determining sample sizes for multilevel models is a complex issue and "rules of thumb" are disputed (Maas & Hox, 2005; Mok, 1995). Furthermore, "effective" sample sizes in MLMs (as opposed to nominal sample sizes) will vary according to the model's predictors (Bickel, 2007). Given the aims and scope of this funding mechanism, the present study is considered preliminary. It will provide pilot data to assess the effectiveness of the BFI as well as exploring the proposed mechanisms of action. The use of repeated measures increases our ability to detect significant relationships. Our results will inform next steps in the investigation of the effectiveness and implementation of the BFI, including a fully powered R01 application to examine the BFI in comparison to an established family-based treatment in a routine VA clinic.

Defining key concepts for analyses:

Treatment dropout: Consistent with past trials of CPT and PE, treatment dropout will be defined by ending treatment prior to the allocated treatment period. In the case of CPT full treatment duration is 12 sessions, while in the case of PE full treatment duration is at least 8 sessions and the concomitant agreement of the therapist that an appropriate ending place has been reached. Any Veteran who ends treatment prior to these milestones will be considered a dropout.

Feasibility/Acceptability: In the current study, feasibility and acceptability will refer to the evaluation and analysis of recruitment, randomization, retention, treatment adherence and fidelity, and use of the BFI with the families of Veterans beginning PTSD treatment. These variables help to determine the acceptability of the treatment and procedures for future studies.

Aim 1: Collect qualitative and quantitative data on feasibility and acceptability of the BFI in a routine care setting.

Hypothesis 1: Levels of feasibility and acceptability of the BFI among Veterans, family members, and clinicians will be high and comparable to levels found in the previous efficacy trial in OCD.

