Hypothesis 2a-2c analytic strategy: Multilevel regression (i.e., hierarchical linear modeling (HLM), growth curve analysis, etc.) will be used to evaluate change in continuous outcome variables (Singer & Willett, 2003). Multilevel regression is a robust method for analyzing change over time, with excellent options for handling missing data, powerful estimation abilities, and flexibility of modeling. This approach will allow for the analysis of an intent-to-treat sample in line with CONSORT guidelines (Altman et al., 2001). For our analysis of change in the variables of interest we will use a multilevel framework in the Mplus program to model time as a Level 1 predictor of the outcome variables (baseline and weeks 6, 12, and 16). We will first specify an unconditional model to ascertain the shape of the change trajectories (e.g., linear versus quadratic change over Time), and will subsequently specify conditional multilevel models to examine treatment effects and the impact of other variables as predictors of individual differences in change. We will also calculate the Cohen's *d* effect size and 95% confidence intervals in order to provide a benchmark for future trials.

o. Literature Cited

Aarons, G. A., Cafri, G., Lugo, L., & Sawitzky, A. (2010). Expanding the domains of attitudes towards evidence-based practice: The Evidence Based Practice Attitude Scale-50. *Administration and Policy in Mental Health and Mental Health Services Research*, 39(5), 331–340. <http://doi.org/10.1007/s10488-010-0302-3>

Boeding, S. E., Paprocki, C. M., Baucom, D. H., Abramowitz, J. S., Wheaton, M. G., Fabricant, L. E., & Fischer, M. S. (2013). Let me check that for you: symptom accommodation in romantic partners of adults with Obsessive-Compulsive Disorder. *Behaviour Research and Therapy*, 51(6), 316–322. <http://doi.org/10.1016/j.brat.2013.03.002>

Borkovec, T.D., & Nau, S.D. (1972). Credibility of analogue therapy rationales. *Journal of Behavior Therapy and Experimental Psychiatry*, 3, 257-260.

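### No test is clearly assigned to treatment dropout, and the two methods named for outcomes that cannot be treated as continuous break down if an arm of about 10 has no dropouts

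*Combined protocol and SAP*

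**What the plan says.** The Data Monitoring Plan (Human Studies section 5a) lists "number of sessions attended/dropout" among the primary outcome measures, beside CAPS-5 and homework ratings. The DATA ANALYSIS section, under Treatment dropout, makes dropout a yes/no status for each Veteran: "Any Veteran who ends treatment prior to these milestones will be considered a dropout".

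Three statements in DATA ANALYSIS bear on how it would be tested.

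- Overview of data analysis: "All quantitative outcomes will be tested at a two-sided" level of .05.
- Hypothesis 2a-2c analytic strategy: multilevel regression "will be used to evaluate change in continuous outcome variables". The same paragraph promises effect sizes with 95% confidence intervals to guide later trials.
- Data checking: where zero-inflation is so heavy that no transformation will serve, the plan for the outcome is "it will be analyzed with logistic regression or generalized estimating equation techniques (appropriate for this small pilot study".

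The Missing data paragraph adds that dropout rates, patterns and timing will be tabulated. No exact or penalised method is named, and the type of test for the logistic model (Wald, likelihood-ratio or other) is not given.

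On size, section (4) Work Proposed says "Phase II will include 20 dyads (N=40"), with half of the family members receiving the BFI. That is about 10 Veterans per arm.

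**The concern.** Reducing dropout is central to the trial's rationale, and greater engagement is part of Hypothesis 2a. A yes/no status does not fit the continuous-outcome model and cannot be transformed to normality. An analyst looking in the plan for another method finds only logistic regression or GEE, which the plan describes as suited to a trial of this size.

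At 10 per arm that description is doubtful. If one arm has no dropouts, the data are separated: the maximum-likelihood odds ratio is zero or infinite, and standard output becomes arbitrary. The better the BFI retains Veterans, the more likely this is. At stake are a usable p-value and interval for one component of the primary outcomes, and protection against choosing among conflicting outputs after the data are seen.

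**Working it through.** The plan gives no power figure or expected p-value for dropout, so there is none to reproduce.

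**Inputs.** From the documents: 20 dyads in Phase II, half receiving the BFI, so 10 v 10; two-sided .05; background dropout that can reach 36% (section (1), Statement of the Problem). Assumed, because the documents give no figure: control dropout of 36%, and true BFI dropout of 5%, 10% or 20%.

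**1. Chance of an empty BFI arm.** P(no dropouts) = (1 − p)^10.
- 5%: 0.95^10 = 0.60
- 10%: 0.90^10 = 0.35
- 20%: 0.80^10 = 0.11

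**2. What each method returns for 0/10 v 5/10.**
- *Logistic regression, Wald test.* The log odds ratio diverges. The empty arm contributes 1/[10p(1 − p)] to its variance, which grows without limit as the fitted p goes to 0. After 20 Newton steps the estimate is −21.20 with SE about 12,710, so z = −0.0017 and p = .999. Stopped at 10 steps, p = .90. The result depends on when the software stops.
- *Logistic regression, likelihood-ratio test.* Log-likelihood with separate arms: 0 + 10 ln 0.5 = −6.931. With a common rate: 5 ln 0.25 + 15 ln 0.75 = −11.247. Statistic: 2 × 4.315 = 8.63 on 1 df, p = .0033.
- *Logit GEE, one record per Veteran.* With model-based standard errors it behaves like the Wald test (p about 1). The robust variance tends to 1/10 for the empty arm plus 1/(10 × 0.5 × 0.5) = 0.4 for control. The SE therefore stays at √0.5 = 0.707 while the estimate diverges, and p falls below 1e-100.
- *Fisher's exact test.* 2 × C(10,5)/C(20,5) = 2 × 252/15,504 = .033.
- *Firth-penalised logistic regression.* Log odds ratio −3.04, p = .011.

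**3. The same across control counts, with no BFI dropouts.**

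| Control dropouts | Wald p (10 / 20 steps) | Likelihood-ratio p | Fisher p | Firth p |
|---|---|---|---|---|
| 4/10 | .90 / .999 | .0105 | .087 | .031 |
| 5/10 | .90 / .999 | .0033 | .033 | .011 |
| 6/10 | .89 / .999 | .0009 | .011 | .003 |
| 7/10 | .89 / .999 | .0002 | .003 | .0009 |
| 8/10 | .88 / .999 | .00004 | .0007 | .0002 |

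Robust GEE gives p below 1e-100 in every row.

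**4. Without an empty arm the Wald test works.** For 1/10 v 6/10 its p is .035, and for 1/10 v 7/10 it is .016.

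**5. Power at 36% control dropout, by enumerating all 11 × 11 tables.**

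| True BFI dropout | Wald power | Fisher power | Share of Fisher-significant results with an empty cell |
|---|---|---|---|
| 10% | 4.8% | 10.7% | 88% |
| 5% | 3.6% | 17.2% | 94% |

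**6. A finite interval is available.** For 0/10 v 5/10 the Wilson 95% limits are 0 to 0.278 and 0.237 to 0.763. The score-type (Newcombe) limits for the difference of 0.50 are 0.50 − √(0.263² + 0.278²) = 0.12 and 0.50 + √(0.263² + 0²) = 0.76.

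**The case against.** A reader might infer that ordinary logistic regression is the only method the plan has for dropout, and that a strong BFI effect would therefore test at p of about 0.9. The documents do not support that, for four reasons.

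- The Data checking sentence also names GEE, which with robust standard errors fails in the opposite direction.
- That sentence is triggered by zero-inflation. Applying it to dropout is an inference. What the text shows is that dropout has no clearly assigned test.
- A p of about 0.9 needs both an empty arm and a Wald test. The plan names no test type, and the likelihood-ratio test of the same model remains usable.
- A strong effect with a single BFI dropout is handled adequately (step 4). At 10% true BFI dropout the BFI arm is non-empty 65% of the time.

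Nor is the method the main reason an effect would be missed. At 36% control dropout the expected control count is about 4, and 0/10 v 4/10 is not significant by Fisher's test either (p = .087). The study calls itself preliminary and will tabulate dropout, so a reader of the results would still see the counts.

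All of this stands, and it limits the point. It does not remove it. The plan commits to testing its quantitative outcomes, so tabulation alone does not meet its own terms. The same 0/10 v 5/10 data can return p = .999, .003 or effectively 0 under methods the plan allows, and none of them supplies a finite odds ratio. If the Data checking sentence is read as not covering dropout, the gap is a missing specification, and the repair is the same.

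**Conclusion.** The point holds as a gap in specification with a practical consequence. Dropout has no clearly assigned test, and the two candidate methods in the plan fail on a plausible result. An empty BFI arm has probability 60%, 35% or 11% at assumed true BFI dropout of 5%, 10% or 20%. The Wald p is then about 0.9 to 1 and the robust GEE p near 0, whatever the control count, and neither method has a finite odds ratio. The likelihood-ratio p-value survives, but it does not supply a finite estimate.

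It would go too far to say that the trial would miss a real dropout effect because of this method. With 36% control dropout, Fisher power is only about 11% (BFI 10%) to 17% (BFI 5%), so sample size is the main limit. The gain from a repair is a valid test and a finite estimate and interval, for one component of the primary outcomes.

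The figures assume 10 Veterans per arm, illustrative dropout rates (the documents give only the 36% upper figure) and, for GEE, one record per Veteran. The change is worth making because it is cheap. It does not call the design into question.

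**What to change.** In DATA ANALYSIS, Data checking, add a rule for dropout and any other yes/no outcome:

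- Report the number of dropouts per arm and the risk difference with a score-type 95% confidence interval.
- Name one exact test in advance, Fisher or Barnard, at two-sided .05.
- If an adjusted model is wanted (the Overview says that unbalanced factors will be controlled for), use Firth-penalised logistic regression with profile-likelihood limits.
- Remove the parenthetical statement that ordinary logistic regression or GEE suits a study of this size.

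Add a cross-reference under Hypothesis 2a-2c analytic strategy so that it is clear which method applies to dropout.

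The cost is a few lines of SAP text and a little code, with no change to design, data collection or sample size. The downside is that exact tests are slightly conservative. Firth estimation may also need software beyond the SPSS and Mplus set-up now named, so its availability should be checked first.

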During the pilot *Phase I* the PI will serve as the BFI clinician. The PI has considerable clinical experience in the treatment of Veterans with PTSD. Additionally, as described above, the PI designed the BFI and has successfully tested its efficacy in a study of patients with OCD and their family members. Beginning in *Phase II* the PI will no longer deliver the intervention; instead, a minimum of 3 clinicians from the VABHS PTSD clinic will be recruited and trained to deliver the BFI.

Comparison condition: Family members in the control or comparison condition of *Phase II* will not receive the BFI or any other study-specific family sessions (aside from the assessments described below). In keeping with the effectiveness aims of the present study, family members in the comparison condition (and the BFI condition) will not be prohibited from receiving any family-inclusive services or sessions that would normally be offered to them in the context of usual VA care.

Independent variables: Receiving or not receiving the BFI (for Veterans/family members); receiving or not receiving training in the BFI (for clinicians).

Dependent variables: Treatment engagement and PTSD symptoms (for patients); accommodation and active treatment support (for family members); qualitative feedback and rates of participation (for Veterans, family members, and clinicians).

Assessment:

Measures and assessment points are shown in Table 1. Qualitative interviews with stakeholders (Veterans, family members, and clinicians) will continue throughout both Phases of the study, as described below. Clinician-rated assessments of Veterans and family members will be completed (in person or via telephone/mail, or a combination of in person and remotely) at baseline and weeks 6, 12, and 16; Veterans and family members will be compensated \$50 for each of these 4 assessment visits that they complete (total of \$200 for the major assessments). Finally, PE and CPT therapists will complete ratings of Veterans' treatment engagement at each session, and will monitor dropout.

Table 1. Assessment Measures and Timepoints

	Time of Administration					
	Baseline	Weeks 0-6	Every PE/CPT session	Week 6	Week 12	Week 16
CAPS-5	X ^v			X ^v	X ^v	X ^v
SCID-5	X ^{v, f}					
Demographics form (Vet/FM)	X ^{v, f}					
Demographics form (Clin)	X ^{tx}					
Relationship information form (Vet)	X ^v					
Relationship information form (FM)	X ^f					
LEC-5	X ^{v, f}					
WTAR	X ^{v, f}					
MOCA	X ^{v, f}					

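### Cohen's d at 10 v 10 dyads is biased about 4% away from zero; reporting Hedges' g as the benchmark removes this at no cost (minor).

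*Combined protocol and SAP*

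**What the plan says.** The last sentence of the Hypothesis 2a-2c analytic strategy plans a Cohen's d "effect size and 95% confidence intervals in order to provide a benchmark for future trials". It names no small-sample correction, no standardising SD and no visit.

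The comparison behind that d is in section (4), Work Proposed: "Phase II will include 20 dyads (N=40) using identical recruitment, inclusion/exclusion criteria, and assessment structure". In this phase "family members will be randomly assigned to receive or not receive the BFI", and the same section puts half of the family members in the BFI arm, so the split is 10 v 10. Under Comparison condition, control relatives "will not receive the BFI or any other study-specific family sessions". The next sentence leaves usual VA family services open to both arms.

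Both power sections call the study preliminary and say its results will inform next steps. The one under DATA ANALYSIS gives as an example "a fully powered R01 application to examine the BFI in comparison to an established family-based treatment in a routine VA clinic".

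**The concern.** Cohen's d divides the mean difference by a sample SD. In small samples this ratio overstates the size of the true standardised difference on average, even with complete data and a perfect model. The plan makes this statistic its stated product for later work, at a sample size where the bias is not quite negligible and the correction is standard. At stake is a benchmark that starts a few per cent too far from zero.

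A second matter is labelling. The only later trial that the plan names has a different comparator, and the plan does not say in words which contrast its d describes.

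**Working it through.** The plan gives no assumed effect, power or sample-size formula, so it has no figure of its own to reproduce. The counts agree: 4 pilot dyads + 20 randomised dyads = 24 dyads = 48 people.

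**Inputs**
- 20 randomised dyads, half per arm: n = 10 v 10 (section (4), Work Proposed).
- Degrees of freedom: m = 10 + 10 - 2 = 18.
- Two-sided 5% level (Overview of data analysis).
- Assumption: d is an end-point difference divided by the pooled two-arm SD. The plan does not say which SD is meant. A model-based d or one divided by the baseline SD would differ somewhat.
- Assumption: a true effect of 0.5 for illustration, with 0.2 and 0.8 as the range. The plan states none.

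**1. Size of the bias**

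J(m) = Γ(m/2) / [√(m/2) × Γ((m-1)/2)]

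J(18) = Γ(9) / [3 × Γ(8.5)] = 40320 / (3 × 14034.4) = 0.958. The usual approximation agrees: 1 - 3/(4 × 18 - 1) = 1 - 3/71 = 0.958.

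The expected value of uncorrected d is the true effect divided by J, and 1/0.9576 = 1.044, so it is 4.4% too large on average.

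| True effect | Mean of d | Bias |
|---|---|---|
| 0.2 | 0.209 | 0.009 |
| 0.5 | 0.522 | 0.022 |
| 0.8 | 0.835 | 0.035 |

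With fewer dyads analysed the bias grows: 5.8% at 8 v 8 and 8.4% at 6 v 6. The plan assumes no attrition rate, so these two are only a range.

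**2. What the correction does**

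g = J × d. An observed d of 0.50 becomes 0.48, and 0.80 becomes 0.77.

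At a true effect of 0.5 the sampling SD of d is 0.483.
- Mean squared error of d: 0.483² + 0.022² = 0.234.
- Mean squared error of g, which is unbiased: 0.9576² × 0.483² = 0.214.
- Reduction: 1 - 0.2143/0.2341 = 8.5%.

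So g is better on both bias and error.

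**3. Bias against imprecision**

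For an observed d of 0.5, t = 0.5 × √(10/2) = 1.118 on 18 df. Inverting the noncentral t gives a 95% CI of -0.40 to 1.38. The Wald check gives SE = √(2/10 + 0.5²/40) = 0.454 and an interval of -0.39 to 1.39. The interval is about 1.8 units wide, against a bias of 0.022. The noncentral-t interval is for the population effect itself, so it is the same whether d or g is printed beside it.

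**4. If the average uncorrected value sized a later trial of the same contrast**

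Assume 80% power, a two-sided 5% level and the normal approximation: n per arm = 15.70/effect².
- At 0.5: 62.8, so 63 per arm.
- At 0.522: 57.6, so 58 per arm, with true power of 77%.

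This is an illustration only. The plan does not state such a use.

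**The case against.** The strongest reply is that 0.022 is trivial against a sampling SD of about 0.48, that the plan already reports a 95% CI with d, and that d v g is largely a reporting convention. The size argument stands and is why the point is minor. It does not defend the uncorrected statistic, because g is better on bias and on mean squared error and costs nothing. The reply that the plan does not name its standardiser also stands. The 4.4% is therefore conditional on the pooled SD.

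A reader might be tempted to infer more. Four such readings are not supported.

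- **The effect is seriously inflated.** Large inflation would arise if d were carried forward only when significant. In a simple end-point t test at 10 v 10 that needs |d| of at least 0.94, and significant results favouring the BFI would average about 1.24 when the truth is 0.5. The plan describes no such selection.
- **The next trial would be undersized.** No section says that d will set any trial's sample size or be its expected difference. Both power sections introduce the named trial as one example of next steps. A single observed d also falls below the truth about half the time (49% at a true effect of 0.5).
- **The control is no treatment.** Usual family services stay open to both arms, and all Veterans are starting PE or CPT.
- **A power loss against an active comparator can be quantified.** Any such figure needs an assumed planning value, an assumed true difference and a superiority aim. The documents give none of these for the later trial.

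A d for the BFI against usual care is a legitimate benchmark for a later trial of that same contrast.

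**Conclusion.** The point holds in a narrow form and is minor. If d is standardised by the pooled SD with all 20 dyads analysed, it is biased away from zero by 4.4% on average (0.009 to 0.035 for true effects of 0.2 to 0.8). Sampling error is far larger and is already disclosed through the planned CI. No test, decision or conclusion within this trial changes.

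The mismatch with the named later trial is a matter of labelling and not an analysis error. This pilot can estimate only the BFI against usual care, and reporting that contrast is correct.

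**What to change.** In the Hypothesis 2a-2c analytic strategy, replace Cohen's d with Hedges' g: d multiplied by the small-sample factor for the degrees of freedom analysed, with a noncentral-t or model-based 95% CI. Name the SD and the visit used, because the factor depends on the SD's degrees of freedom.

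As an optional clarification, add one sentence saying that the estimate compares the BFI with usual care without study family sessions, and that it does not estimate the difference between the BFI and an established family treatment.

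The cost is a wording change and one multiplication. The reported effect becomes about 4% smaller (1 - 0.958 = 0.042), and no new data, participants or procedures are needed.
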